2. INTRODUCTION

2.1. BACKGROUND AND RATIONALE

Wound healing is known to be assisted by the removal of necrotic tissue.¹ Healing of these wounds may not occur at an optimal rate due to the presence of such necrotic tissue. Honey has been known to be an important adjunctive therapy in the field of wound care for centuries.^{2,3} Honey impregnated wound dressings serve as autolytic debridement agents that promote removal of necrotic tissue from wounds, while maintaining a moist healing environment in subjects with chronic wounds.

The purpose of this study is to evaluate the effectiveness of a honey-impregnated wound dressing (TheraHoney[®] Foam Flex, Medline Industries, Inc.) at removing necrotic tissue in subjects with chronic foot or ankle wounds. The study will also evaluate the ability to promote granulation and re-epithelialization when using this type of dressing, as well as collect safety and ease of use data on the product.

2.2. INVESTIGATIONAL PRODUCT: THERAHONEY[®] FOAM FLEX

The investigational product being examined, TheraHoney[®] Foam Flex, contains 100% Manuka honey and is ideal for difficult to dress wounds. The dressing provides a moist wound environment to help promote autolytic debridement. TheraHoney[®] Foam Flex is ideal for partial or full thickness wounds with moderate-to-heavy drainage. The honey in the product is carefully filtered, irradiated, and tested in a laboratory.

Suitable secondary dressings are indicated for use when necessary. Contraindications include third-degree burns and lesions with active vasculitis. More information on the product, including labeling, is provided in Appendix A.

2.3 STUDY POPULATION AND DURATION

Participants in this study will be patients with chronic foot or ankle wounds who are under the care of a physician (the Principal Investigator or a Co-Investigator; collectively an “Investigator” or “the Investigators”). Further information on study population can be found in section 4.2. Following initial screening, this study protocol calls for a 4-week period that encompasses initial application of wound dressing, weekly follow-up visits, and a final assessment at approximately 4 weeks. In the event a patient’s wound heals sooner than 4-weeks and he/she no longer needs medical care, all necessary data to complete the study will be collected at the visit where an Investigator deems the patient to be healed, and he/she will not continue through 4-weeks. Therefore, study duration period may vary based on individual wound response and discretion of an Investigator, but will not exceed 4-weeks plus screening time.

2.4 STUDY RISKS AND BENEFITS

This study presents minimal risk to the participant sample, given that this is a currently marketed medical device with FDA cleared 510(k) pre-market submission that will be used in accordance with the product's labeling. Participants may experience some discomfort when applying or removing the dressing, but this should be minimal and not exceed what they would feel through the normal use of the product. Participants may directly benefit from their participation in this study, as the TheraHoney® Foam Flex dressing may provide better debridement and healing of their wound than their previous therapies, though this is not guaranteed and a comparison to other therapies is not part of this study's scope. Participation in this study may allow for scientists and healthcare professionals to better understand the clinical utility of honey impregnated dressings, thereby informing future clinical practice.

3. STUDY OBJECTIVES

3.1. PRIMARY OBJECTIVE

To evaluate the ability of TheraHoney® Foam Flex wound dressing to remove necrotic tissue in patients with chronic foot or ankle wounds.

3.2. SECONDARY OBJECTIVES

To evaluate the efficacy of TheraHoney® Foam Flex in the promotion of granulation and re-epithelialization in chronic wounds.

To evaluate the safety and ease of use of TheraHoney® Foam Flex when applied to chronic wounds.

4. STUDY DESIGN

4.1. DESIGN

A single-center, open-label, observational study involving 20 evaluable subjects with qualified chronic foot or ankle wounds (as judged by an Investigator, in reference to the product labeling and inclusion criteria listed below) on which treatment with TheraHoney® Foam Flex will be administered in order to evaluate product efficacy, safety, and ease of use.

4.2. SUBJECT SELECTION

4.2.1. Inclusion Criteria

Subjects MUST MEET ALL of the following criteria prior to enrollment:

- Male or female ≥ 18 years of age
- Written consent must be obtained from the subject and/or their legally-authorized representative.
- Subject has a qualified chronic foot or ankle wound, sized 1 cm^2 to 25 cm^2 , for ≥ 4 weeks in duration.
- Must have necrotic tissue at least 20% of wound area
- The wound type matches one of the indicated wounds listed on the product labeling:
 - Leg ulcers
 - Pressure ulcers
 - Diabetic foot ulcers
 - First and second degree burns
 - Surgical wounds
 - Trauma wounds
- Subject has adequate circulation as demonstrated by biphasic or triphasic Doppler waveform, consistent with adequate blood flow, within 3 months prior to study enrollment. If monophasic on exam, then non-invasive tests must display Ankle Brachial Index over 0.8 and no worse than mild disease on segmental pressures.
- Subject is likely to be compliant with instructions for care, such as following institutional standard of care directions, offloading, and keeping the wound area protected from environmental contaminants
- Type I/II diabetic subjects that meet the following criteria:
 - Random blood glucose is less than 450 mg/dL within 30 days of the screening visit

4.2.2. Exclusion Criteria

Subjects MUST NOT MEET ANY of the following criteria prior to enrollment:

- Subject has a known sensitivity or allergy to honey based products, bee venom, or other ingredients in product
- The subject is breastfeeding, pregnant, or has intentions of becoming pregnant during the course of their study participation.
- Wound duration ≥ 52 weeks

- The subject has a prognosis that indicates unlikely survival past the study period.
- The subject is currently receiving dialysis.
- Gangrene is present in the target wound.
- Patient's wound is infected
- The subject's diagnosis indicates third degree burns.
- The subject has received any treatment prior to study enrollment that may, in the opinion of an Investigator, affect the outcome of the study.
- In the opinion of an Investigator, the subject is otherwise not suitable for study participation, such as the subject is likely to be non-compliant with study requirements.

5. STUDY PROCEDURES

5.1. RECRUITMENT

Subjects will be recruited from the Northern Illinois Foot and Ankle practice of the Principal Investigator (PI) or co-Investigators. All interested subjects will undergo informed consent and screening to ensure they meet the inclusion/exclusion criteria listed in Sections 4.2.1 and 4.2.2 of this protocol.

5.2. SCREENING VISIT (DAY 0)

5.2.1. Informed Consent

Written consent must be obtained from all participating subjects and documented on an informed consent form (ICF) that has received approved by an IRB/Ethics Committee. The ICF must be written in adherence to Good Clinical Practice (GCP) and comply with all elements required by FDA CFR 50.25 and ICH 4.8, state and local regulations, and additional elements relevant to specific study situations, (including a statement that Medline Industries, Inc. and authorities have access to subject records).

5.2.2. Demographics

Subject age, gender, and race will be captured.

5.2.3. Medical History and Concomitant Medication

During initial consideration to determine eligibility, a generalized medical history must be obtained from the subject in order to determine whether any previous or current co-morbidities, chronic wounds (if known) and/or treatments that may, in the opinion of an Investigator, adversely affect subject safety and/or the outcome of study data (reference exclusion criteria listed in section 4.2.2.).

A record of relevant medications (prescription and over the counter) that are administered to the subject throughout the duration of their study participation should be noted, such as antibiotic use and any ongoing adjunct wound therapies. Careful consideration should be made to investigate and document medication use that may be related to Adverse Event occurrences. Additional information regarding Adverse Event reporting may be found in Section 7.

5.2.4. Vascular Ankle Assessment

Doppler Ultrasound (biphasic or triphasic wave form) will be used to assess vascular supply. In the event the potential subject does not have a reading within the past 90 days prior to the screening visit, the assessment will take place at the screening visit using a SONOTRAX Basic ultrasonic pocket Doppler by Edan Industries Inc. If exam result is monophasic, subject can still be enrolled in study if non-invasive tests display an Ankle Brachial Index over 0.8 and no worse than mild disease on segmental pressures.

5.2.5. Diabetic Assessments

Subjects with diabetes (type I or II) will be allowed to participate in the study, provided that their glucose level results are less than 450 mg/dL. In the event the potential subject does not have a blood glucose reading within the past 30 days, a measurement will be conducted at the screening visit using an EVENCARE G3 blood glucose monitoring system.

5.2.6. Wound Screening Evaluation

The type of wound will be diagnosed and receive a diagnostic code based on type of wound at initial presentation (e.g., venous, diabetic, pressure, etc.). A history of the wound will be collected to determine that it has been present for greater than four weeks, but less than 52 weeks. Further, every attempt should be made to document the types of dressings previously used in the treatment of the wound in question, up to six months prior to enrollment. An image of the wound will be taken with the eKare inSight® wound assessment camera, which will calculate wound size and tissue composition of the wound. The Investigator will analyze the wound and the image of the wound to confirm wound size and percent necrotic tissue in order to verify the wound meets the inclusion criteria stated above.

5.2.7. Confirmation of Eligibility

The subject is confirmed as meeting all required inclusion criteria, as listed in section 4.2.1.

The subject is confirmed as not meeting any of the exclusion criteria, as listed in section 4.2.2.

5.3. INITIAL VISIT (DAY 1) AND WEEKLY INTERIM VISITS

Please note that the Initial Visit (Day 1) may be combined with the Screening Visit (Day 0) for pragmatic purposes. In the event this occurs, all Screening Visit activities will precede any Initial Visit activities.

5.3.1. Wound Evaluation

Wound evaluation for data collection purposes will begin at the initial visit and thereafter during each visit at the outpatient centers where this study is going to be conducted. Wound Evaluation will include the following parameters (please also see sample Case Report Form (CRF) in Appendix D which will be used at each visit):

- Wound size (length, width and depth)
- Evaluation of Odor. Investigator assessment of wound odor will be captured via a 4-point categorical scale after each application.
- Percent of Necrotic Tissue. The percent of necrotic tissue will be assessed based on photos taken of the wound with eKare inSight® and visual confirmation from the Investigator to determine the percent covered with the necrotic tissue versus the total area of the wound. This will be entered in question six of the Bates-Jensen Wound Assessment Tool, as described in Appendix C.
- Pain Assessments. Pain will be assessed by the subject after the application (or re-application, for interim visits) of the dressing. Pain will be based on a 10-point Pain Score.
- Site Infections. Any infections at the wound site will be documented. In the event a participant develops an infection his/her participation in the study will discontinue, and the physician will implement appropriate treatment measurements.
- Bates-Jensen Wound Assessment Tool (BWAT). The BWAT will be administered to further characterize the wound. Please see Appendix C for BWAT.

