5.3.5. TheraHoney® Foam Flex Application

The application of TheraHoney® Foam Flex will be performed according to the product labeling during the Initial Visit (Day 1) and subsequent Interim Visits. Dressing changes will take place daily, with the Investigator instructing participants on how to change the dressing at home on days when they do not visit the clinic. The use of secondary dressings will also be done at the discretion of an Investigator. At the discretion of an Investigator, use of TheraHoney® Foam Flex should be discontinued due to adverse events or lack of wound closure response.

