5.4.1. Data collection

All activities listed in section 5.3.1 and 5.3.2 will take place in the Final Visit in order to complete data collection. Notations on dressings and debridement will not be documented at this visit, though they may of course occur based on an Investigator's judgment.

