5.4.2. Physician Questionnaire

Product ease of use will be evaluated using on the Investigator Questionnaire (Appendix E) at the end of subject's study participation.

TABLE 5.1 TIME AND EVENTS SCHEDULE

REQUIRED ASSESSMENTS	SCREENING VISIT Day 0 (May be combined with first interim visit, Day 1)	INITIAL VISIT Day 1	INTERIM VISITS Approx. Every 7 Days	FINAL VISIT ⁵ Approx. 28 days after Day 1 visit
Informed Consent	X			
Demographics	X			
Medical History	X			
Concomitant Medication	X			
Physical Examination	X			
Doppler Assessment	X ^{1,3}			
Blood Glucose Assessment	X ^{1,2,4}			
Wound Screening Evaluation	X			
Confirmation of Eligibility	X	X	X	
Adverse Event Assessment	X	X	X	X
Wound Evaluation		X	X	X
Wound Photograph		X	X	X
TheraHoney® Foam Flex		X	X	
Secondary Dressing Notation		X ¹	X ¹	
Mechanical debridement noted		X ¹	X ¹	
Investigator Questionnaire				X

¹If required

²Within 30 days of screening visit or at screening visit

³Within 90 days of screening visit or at screening visit

⁴Diabetic subjects only

⁵Final visit may be an interim visit in the event patient heals fully before 4 weeks and no longer requires treatment

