10.1 APPENDIX A: Therahoney® Product Labeling

MANUKA HONEY

ADVANCED WOUND CARE

THERAHONEY® FOAM FLEX is ideal for moderate to heavily exuding wounds.

- With 100% Leptospermum Scoparium honey from New Zealand
- Maintains moist wound healing environment that allows autolytic debridement of necrotic tissue

INSTRUCTIONS FOR USE:

1 Remove dressing from package. Remove one piece of the release liner.
Note: Use a dressing large enough to cover the wound and surrounding skin.

2 Place dressing on the wound and remove the other release liner.

3 Secure in place using tape or a secondary dressing.

ADDITIONAL CONSIDERATIONS: For Large wounds use additional dressings placed side by side. Dressings may be cut to size if needed.

INDICATIONS FOR USE: Therahoney® Foam Flex dressings are for use in moist wound management of: leg ulcers, pressure ulcers, 1st and 2nd degree burns, diabetic foot ulcers, surgical wounds, trauma wounds. A moist environment allows autolytic debridement of necrotic tissue.

CHANGE FREQUENCY: Therahoney® Foam Flex dressings may require a daily application depending on wound exudate, any surrounding interstitial fluid, edema, and dressing protocol.

STORAGE: Protect from freezing, avoid excessive heat.

CONTRAINDICATIONS: There is no record of increased blood sugar levels in patients with diabetes due to the use of honey dressings however it is advisable to monitor the levels during use of Therahoney® Foam Flex. Temporary increased pain may be experienced due to osmotic action and/or low pH of honey. If pain persists, discontinue use of the dressing and gently irrigate the wound with sterile saline solution. Do not reuse.

CAUTION: Federal (USA) law restricts this device to sale by or on the order of a physician or properly licensed healthcare professional.

Sterile in unopened, undamaged package. Single use only.

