10.4 APPENDIX D: Case Report Form

Case Report Form (R16-017)

Subject Number:	Visit Date:	Visit Time:	AM	PM	Visit Type and Number:	
Height (inches):	Weight (lbs):	Age:				
Sex:  Male	 Female					
Race:  White	 Black	 Hispanic or Latino	 Asian	 Other/Mixed Race	 Native American	
Was mechanical debridement used?  Yes		 No				
Was a secondary dressing used?  Yes		 No	If yes, what kind? _____			
Wound Assessment						
Physical Examination and Wound Zoom Analysis			Bates – Jensen Wound Assessment Tool (BWAT)			

Diagnosis: _____
 
What is the percent of necrotic tissue? _____ %
 
Wound size (cm): Width _____ x Length _____ x Depth _____
 
Evaluation of odor: _____
 
 1  2  3  4
 
VAS Pain scale score within 10 minutes following dressing change: _____
 
 0  1  2  3  4  5  6  7  8  9  10
 
Site Infection: Yes No
 
If yes, discontinue subject and note steps taken:
			
1. Skin: _____
 
2. Depth: _____
 
3. Edges: _____
 
4. Undermining: _____
 
5. Necrotic Tissue Type: _____
 
6. Necrotic Tissue Amount: _____
 
7. Exudate Type: _____
 
8. Exudate Amount: _____
 
9. Skin Color Surrounding Wound: _____
 
10. Peripheral Tissue Edema: _____
 
11. Peripheral Tissue Induration: _____
 
12. Granulation Tissue: _____
 
13. Epithelialization: _____
 
TOTAL BWAT SCORE: _____
			

Place photograph of the wound from the Wound Zoom camera below:

Subject #: _____ **Date:** _____

*Please note that the information in the picture should match the above information.

Signature _____ **Date** _____

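### Odor and pain are timed to a dressing application that is not scheduled at the Final Visit, so final scores may be taken under different, unrecorded conditions, and no score precedes treatment.

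*Combined protocol and SAP*

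**What the plan says.** **Timing of the scores.** Section 5.3.1 states for odor: "Investigator assessment of wound odor will be captured via a 4-point categorical scale after each application". For pain it states: "Pain will be assessed by the subject after the application (or re-application, for interim visits) of the dressing". The pain wording covers Day 1 and the interim visits and does not mention the Final Visit. The CRF in Appendix D, used at each visit, asks for "VAS Pain scale score within 10 minutes following dressing change". It does not name the product.

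**Scheduled applications.** Section 5.3.5 places clinic application of the product "during the Initial Visit (Day 1) and subsequent Interim Visits". In Table 5.1 the product row is marked for the Initial and Interim Visits and is blank for the Final Visit.

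**Final Visit.** Section 5.4.1 states: "All activities listed in section 5.3.1 and 5.3.2 will take place in the Final Visit". Odor and pain are among those activities. The same section says that dressings and debridement may occur at that visit but will not be noted. Under section 5.4, if a wound is judged fully healed at an interim visit and needs no more care, that visit becomes the Final Visit.

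**Before treatment.** The screening evaluation in section 5.2.6 covers diagnosis, wound history, previous dressings and an image. It includes no odor or pain score. In Table 5.1 the wound evaluation starts at the Initial Visit.

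**Analysis.** Section 8.3.2 lists mean odor score and mean pain score, each with a 95% confidence interval. It names no visit and no change from Day 1.

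**Label.** Appendix A warns: "Temporary increased pain may be experienced due to osmotic action and/or low pH of honey".

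**The concern.** Both scores are mandatory at a visit where the event that times them is not scheduled. Site staff have to improvise. One subject may be re-dressed and then scored, another scored with the wound open, and a third scored on healed skin with nothing applied. Because dressings at that visit are not noted, the analyst cannot tell these cases apart. Whether a dressing is applied can also depend on how well the wound did, so the scoring condition may be tied to the outcome.

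For pain the label makes this matter. A Day 1 score taken within minutes of a fresh honey dressing may include temporary application pain, and a Final score taken without one would not. Read side by side, the two would tend to overstate improvement. Averaging over visits would mix the two conditions.

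Separately, the first odor and pain scores both follow the first application, so no scheduled score describes the wound before treatment. That cannot be recovered once the subject has been treated.

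**Working it through.** The documents give no figure for odor or pain, and no power calculation, so there is nothing of the plan's own to reproduce. The check has two parts.

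**1. Conditions at each visit**

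| Visit | Product application scheduled | Odor and pain required | Timing defined | Dressing noted |
|---|---|---|---|---|
| Screening (if separate) | No | No | – | – |
| Initial, Day 1 | Yes (5.3.5, Table 5.1) | Yes (5.3.1) | After application | Secondary dressing, yes |
| Interim | Yes (5.3.5, Table 5.1) | Yes (5.3.1) | After re-application | Secondary dressing, yes |
| Final | No (5.3.5, Table 5.1) | Yes (5.4.1) | No scheduled event to anchor it | No (5.4.1) |

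Day 1 and interim scores share one stated timing. The Final score does not, and the record will not show what was done. No row gives a score before the first application.

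**2. How large the effect on pain could be (illustration only)**

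This assumes an analysis that the plan does not state: the mean Day 1-to-Final reduction with a t interval, read as a reduction when the lower limit is above zero.

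Inputs:
- n = 20 evaluable subjects (sections 4.1 and 8.2).
- True change = 0 (assumed).
- Application effect d = 0.5, 1 or 2 points, present at Day 1 and absent at Final in every subject (assumed; the label gives no size).
- SD of the change = 2 or 3 points (assumed; the documents give none).

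Formulas:
- Critical value t(0.975, 19 df) = 2.093.
- Interval half-width = 2.093 × SD / √20 = 0.468 × SD, which is 0.94 points at SD 2 and 1.40 at SD 3.
- Probability of a spurious reduction = P(T > 2.093), where T is noncentral t with 19 df and noncentrality (d / SD) × √20.

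| d (points) | SD 2: noncentrality | SD 2: probability | SD 3: noncentrality | SD 3: probability |
|---|---|---|---|---|
| 0 | 0 | 2.5% | 0 | 2.5% |
| 0.5 | 1.118 | 18% | 0.745 | 11% |
| 1 | 2.236 | 56% | 1.491 | 29% |
| 2 | 4.472 | 99% | 2.981 | 81% |

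For d = 1 the probability is 40% at SD 2.5 and 18% at SD 4.

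If pain were instead averaged over about five visits (assumed: Day 1, three interim, Final), a 1-point shift at the Final Visit alone would move a subject's mean by 1/5 = 0.2 points.

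No calculation is offered for odor, because the documents say nothing about how a dressing affects it.

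**The case against.** The strongest reply is that no bias has been shown. Section 8.3.2 asks only for mean scores with an interval. Wound volume, in the same list, is described as a change over time, so the plan names change where it means change. The rule that a positive lower limit indicates a significant reduction belongs to the primary endpoint. This stands: the percentages above apply to an analysis that the plan does not contain, with assumed shifts and SDs.

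Second, section 5.4.1 allows a dressing at the Final Visit, and the CRF ties pain to any dressing change. An open wound may well be re-dressed and then scored much as before. This also stands, so a reader who infers that the Final scores are necessarily taken without a dressing goes too far. It does not remove the defect: whether a dressing was applied is left open, and the answer is not recorded.

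Third, pain after application is a sensible tolerability measure, given the secondary objective on safety and ease of use in section 3.2 and the discomfort foreseen in section 2.4. That is a reason to keep it, but not to have it as the only pain score. Section 8.3 lists pain under efficacy.

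Fourth, a reader might infer that odor is rated through a fresh dressing and so is masked until the Final Visit. The documents do not support that. They do not say whether the wound is covered when odor is rated, or that a dressing changes the rating.

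**Conclusion.** The concern holds in a limited form. Following the plan as written, odor and pain at the Final Visit have no defined timing. They may be taken under conditions that differ from Day 1 and interim visits, and the record cannot show which. No score is scheduled before the first application.

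It would be tempting to conclude that both secondary endpoints are biased or say nothing about the wound. The documents do not support that. Neither endpoint is defined as a Day 1-to-Final comparison, and the Day 1 and interim scores are consistent with each other. Distortion is conditional on comparing Day 1 with Final or pooling visits. For pain its likely direction, an overstated improvement, rests on the label warning. For odor neither direction nor size can be stated.

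The size for pain is unknown. Under the assumed change analysis, a 1-point application effect gives a spurious reduction in about 56% of trials at SD 2 and about 29% at SD 3, against 2.5% nominally. These figures also assume that no subject is re-dressed before the Final score; a mixture would give a smaller average shift. The endpoints are secondary, but the lost information cannot be recovered and the remedy is cheap, so the change should be made.

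**What to change.** - Reconcile sections 5.3.1, 5.3.5 and 5.4.1, Table 5.1 and the Appendix D CRF on when odor and pain are scored, including at the Final Visit.
- Rate both at every visit, including Day 1 before the first application and the Final Visit, at one fixed point: after any old dressing is removed and before any new one. For a healed wound with no dressing, rate at the start of the assessment.
- Keep the existing post-application pain score as a separate tolerability measure.
- Record on the CRF whether a dressing was applied at the Final Visit.
- In section 8.3.2, use the pre-dressing scores and name the visit and contrast: change from Day 1 to Final, with its 95% confidence interval.

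The cost is CRF wording, a dressing entry at the Final Visit and one extra pain question to the subject per visit. No extra visits or subjects are needed.
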